6.3.1 Adverse Events by Demographics and Baseline Characteristics

For the AE(s) by demographics and baseline characteristics in the safety analysis set:

- The number of subjects to whom AE occurred and the number of AEs will be calculated.
- The incidence proportion of AEs and its 95% confidence interval will be estimated. Chi-square test or Fisher's exact test will be used for comparing between subcategories of each demographics and baseline characteristics.
- If necessary, analysis for the impact of the safety may be carried out using logistic multiple regression analysis. In general, the variables corresponding to the baseline characteristics listed in section 6.1 are used as an independent variable. However, as considering the structure and characteristics of the collected data, the variables used for the actual analysis can be added or subtracted.

	CONFIDENTIAL :	Last Update Date
	THIS DOCUMENT AND INFORMATION CONTAINED HEREIN IS PROPRIETARY TO COMPANY AND IS NOT TO BE DISCLOSED WITHOUT THE WRITTEN PERMISSION OF COMPANY.	21-AUG-2017
STATISTICAL ANALYSIS PLAN(V3.0)		

6.3.2 Adverse Events by Preferred Terms

All AEs recorded in the CRF will be classified by body organs and terms under the classification standard of MedDRA terms, and all AEs excluding the AEs where causal relationship with Trajenta is “Unlikely” will be treated as AEs which causality cannot be excluded (hereafter “Adverse Drug Reaction(ADR)”).

For subjects to whom AE occurred, the incidence proportion of AEs and the number of AEs will be summarized.

Details are as follows.

- ① The frequency and percentage of the number of AEs according to serious adverse event, intensity, outcome of the event, action taken, causality, therapy of the event will be calculated.
- ② All AEs will be classified into the preferred terms according to serious adverse event, intensity, outcome of the event, action taken, causality, therapy of the event. The frequency and percentage of the number of each AE will also be calculated.
- ③ The number of subjects and the number of AE/ADR, Serious AE/Serious ADR, unexpected AE/ADR, unexpected Serious AE/unexpected Serious ADR will be calculated according to the preferred terms. In this case, the following subgroups are presented separately. Also, the incidence proportion and its 95% confidence interval will be estimated.
 - All of safety analysis set
 - Short-term effectiveness analysis set (Administration of Trajenta less than 24 weeks)
 - Long-term effectiveness analysis set (Administration of Trajenta for 24 weeks or more)
 - Subjects in effectiveness analysis set who administered DPP-4 inhibitor before administration of Trajenta
 - Subjects in effectiveness analysis set who did not administer DPP-4 inhibitor before administration of Trajenta
- ④ Preferred terms of Serious AE/Serious ADR, unexpected AE/ADR will be presented respectively according to the proportion of AE in the local product document.
- ⑤ For subjects excluded from the safety analysis set[†], the number of subjects and the number of AE/ADR, Serious AE/Serious ADR, unexpected AE/ADR, unexpected Serious AE/unexpected Serious ADR will be calculated according to the preferred terms. Also, the incidence proportion and its 95% confidence interval will be estimated.

[†]Subject excluded from safety analysis set: ‘Subjects who have not taken Trajenta’ and ‘Follow-up failure’ of patients excluded from safety analysis sets will be excluded (Reflecting the Ministry of Food and Drug Safety (MFDS) guideline).

	CONFIDENTIAL :	Last Update Date
	THIS DOCUMENT AND INFORMATION CONTAINED HEREIN IS PROPRIETARY TO COMPANY AND IS NOT TO BE DISCLOSED WITHOUT THE WRITTEN PERMISSION OF COMPANY.	21-AUG-2017
STATISTICAL ANALYSIS PLAN(V3.0)		

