7.4 HANDLING OF MISSING DATA

As this is non-interventional study, there are no required investigations and diagnostic procedures (e.g. lab, ultrasound).

Maximum attempt will be made to ensure the completeness of data collection. All available data will be used in the data analysis. There will be no imputation of data to fill the missing values.

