3.1 Safety Analysis Set

Subjects who administrated Trajenta at least once will be included in the safety analysis set.

Reflecting MFDS guideline, the subjects below shall be excluded from safety analysis set in the following order:

- (1) Subjects administered Trajenta prior to the contract date
- (2) Subjects who have not taken Trajenta
- (3) Follow-up failure: The subjects whose safety follow up have not been completed
- (4) Subjects who were prescribed for other indications except target indication:
 - [Target indication]
 - Patients with type 2 diabetes mellitus

	CONFIDENTIAL :	Last Update Date
	THIS DOCUMENT AND INFORMATION CONTAINED HEREIN IS PROPRIETARY TO COMPANY AND IS NOT TO BE DISCLOSED WITHOUT THE WRITTEN PERMISSION OF COMPANY.	21-AUG-2017
STATISTICAL ANALYSIS PLAN(V3.0)		

- (5) Subjects who violated inclusion/exclusion criteria
- (6) Subjects who did not follow dosage/capacity
 - [Dosage/Capacity]
 - The recommended dose 5 mg once daily
 - Administration by monotherapy
 - Combination with metformin
 - Combination with sulfonylurea
 - Combination with both sulfonylurea and metformin
 - Combination with insulin
 - Combination with both insulin and metformin
 - Combination with both empagliflozin (25mg) and metformin
- (7) Subjects of contraindications
 - Who are hypersensitive to the principle components and additives of this product
 - Patients with type 1 diabetes or diabetic ketoacidosis
- (8) Subjects who are not Korean

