3.2 Effectiveness Analysis Set

The subjects below shall be excluded from effectiveness analysis set in the following order:

- (1) Subjects who excluded from safety analysis set
- (2) Missing HbA1c value at both baseline and after administration of Trajent

4. Endpoints

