6.3 Safety Analyses

In the safety analysis set, the number of subjects with AEs and the number of AEs will be calculated. Also, the incidence proportion of AEs will be estimated with its 95% confidence interval.

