7.4 Safety Analyses

- According to the baseline characteristics, incidence proportion and the number of AEs (frequency and percentage)
- The number of AEs for serious adverse event, intensity, outcome of the event, action taken, causality, therapy of the event (frequency and percentage)
- The number of AEs for serious adverse event, intensity, outcome of the event, action taken, causality, therapy of the event by preferred terms (frequency and percentage)
- For safety analysis set, according to whether or not administered Tragenta for more than 24 weeks and whether or not administered DPP-4 inhibitor before administration of Trajenta, the number of AE/ADR, Serious AE/Serious ADR, unexpected AE/ADR, unexpected Serious AE/unexpected Serious ADR by preferred terms (frequency, percentage, incidence proportion and its 95% confidence interval)
- Preferred terms of Serious AE/Serious ADR, unexpected AE/ADR according to the proportion of AE

	CONFIDENTIAL :	Last Update Date
	THIS DOCUMENT AND INFORMATION CONTAINED HEREIN IS PROPRIETARY TO COMPANY AND IS NOT TO BE DISCLOSED WITHOUT THE WRITTEN PERMISSION OF COMPANY.	21-AUG-2017
STATISTICAL ANALYSIS PLAN(V3.0)		

- For subjects excluded from the safety analysis set[†], the number of AE/ADR, Serious AE/Serious ADR, unexpected AE/ADR, unexpected Serious AE/unexpected Serious ADR according to the preferred terms (frequency, percentage, incidence proportion and its 95% confidence interval)
- Multiple logistic regression analysis on the incidence proportion of AEs
 - †Subject excluded from safety analysis set: ‘Subjects who didn’t receive Trajenta’ and ‘Follow-up failure’ of patients excluded from safety analysis sets will be excluded (Reflecting the Ministry of Food and Drug Safety (MFDS) guideline).

8. Note

- Each statistical analysis will be carried out with SAS Software version 9.4 or more recent version.
- In the descriptive statistics, mean, SD, median, minimum and maximum will be calculated for continuous variables, and frequency and percentage for categorical variables.
- Data including sign of inequality such as “≥20”, “>20” will be excluded from analysis.
- All test statistics will be the results of two-sided tests with the statistical significant level of 0.05.
- The followings shall be included only in re-examination report:
 - Estimation of 95% confidence interval for incidence proportion of AEs by baseline characteristics

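### SAP 6.3.2 takes four of five safety subgroups from the effectiveness set, SAP 7.4 lists the same tables for the safety set, and the 24-week cut is worded two ways

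*SAP*

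**What the plan says.** SAP 6.3 sets the population for safety: "In the safety analysis set, the number of subjects with AEs and the number of AEs will be calculated". SAP 6.3.1 does the same for the breakdown by baseline characteristics: "For the AE(s) by demographics and baseline characteristics in the safety analysis set". Protocol 7.3.1 bases safety analyses on every patient who received at least one dose, with no condition on HbA1c.

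SAP 6.3.2 item 3 then tabulates AEs and ADRs, serious, unexpected and unexpected serious, by preferred term in five groups. The first is the full safety set. The second is "Short-term effectiveness analysis set (Administration of Trajenta less than 24 weeks". The third is its long-term counterpart, and the last two are effectiveness-set patients with and without earlier DPP-4 inhibitor use.

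SAP 7.4, which lists the outputs, describes the same tables with the same two splits but opens "For safety analysis set, according to whether or not administered Tragenta for more than 24 weeks".

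The effectiveness set (SAP 3.2) is the safety set less patients meeting one further condition: "Missing HbA1c value at both baseline and after administration of Trajent". On laboratory data, protocol 7.4 states: "As this is non-interventional study, there are no required investigations and diagnostic procedures (e.g. lab, ultrasound".

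**The concern.** Safety is the primary objective. Item 3, with its listing in 7.4, is the only place where preferred-term AE, ADR, serious and unexpected event incidences are split by treatment duration and prior DPP-4 inhibitor use. Under 6.3.2, whether a patient counts in those splits depends on having a glycaemic laboratory value. The SAP gives no reason for this.

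Three things follow. The subgroups need not add up to the overall group shown with them. Their denominators can differ from the duration breakdown in 6.3.1, which uses the safety set. And because the SAP does not say whether section 6 or section 7 prevails, two programmers could each follow it and deliver different tables.

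**Working it through.** **1. Population named for each part of the safety analysis**

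| Place | Population |
|---|---|
| SAP 6.3, overall AE incidence | Safety set |
| SAP 6.3.1, AEs by baseline characteristics, including long-term administration | Safety set |
| SAP 6.3.2 item 3, overall group | Safety set |
| SAP 6.3.2 item 3, short-term | Effectiveness set |
| SAP 6.3.2 item 3, long-term | Effectiveness set |
| SAP 6.3.2 item 3, prior DPP-4 inhibitor | Effectiveness set |
| SAP 6.3.2 item 3, no prior DPP-4 inhibitor | Effectiveness set |
| SAP 7.4, the item 3 tables | Safety set |

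Four of the five item 3 groups carry the effectiveness label. This applies to all eight event categories that the item names: AE, ADR, and the serious, unexpected and unexpected serious version of each.

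**2. Which patients are affected**

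Patients without completed safety follow-up are not the issue. SAP 3.1 removes them from the safety set ("Follow-up failure: The subjects whose safety follow up have not been completed"), and SAP 3.2 carries that exclusion into the effectiveness set. The affected patients are those in the safety set who fail the HbA1c condition of SAP 3.2.

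Item 5 of 6.3.2 does not recover them, because it starts "For subjects excluded from the safety analysis set" and these patients are not excluded from that set. Within the item 3 tables, their events appear in the overall group and in no subgroup.

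**3. Additivity**

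Assume that duration and prior DPP-4 inhibitor use are known for everyone.

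- All groups from the safety set: short-term + long-term = overall, and prior + no prior = overall.
- As 6.3.2 is written: each pair adds up to the effectiveness set only.

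**4. Size of the effect on incidence**

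Let m be the share of a subgroup's safety-set patients removed for HbA1c. Let p_kept and p_removed be the AE incidences in the two parts.

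- p_full = (1 − m) × p_kept + m × p_removed
- p_kept − p_full = m × (p_kept − p_removed)

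Both incidences lie between 0 and 1, so the shift is at most m in either direction. The documents give neither m nor the incidences. The table below is an illustration on assumed values only: 3,000 patients (the planned enrolment, taken here as the safety set) and p_kept = 10%. It treats each pair of subgroups together.

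| Assumed m | Assumed p_removed | Patients with an AE absent from each pair | Safety-set incidence | Effectiveness-set incidence |
|---|---|---|---|---|
| 5% | 10% | 150 × 0.10 = 15 | (285 + 15)/3,000 = 10.0% | 10.0% |
| 5% | 30% | 150 × 0.30 = 45 | (285 + 45)/3,000 = 11.0% | 10.0% |
| 10% | 20% | 300 × 0.20 = 60 | (270 + 60)/3,000 = 11.0% | 10.0% |
| 10% | 30% | 300 × 0.30 = 90 | (270 + 90)/3,000 = 12.0% | 10.0% |
| 30% | 30% | 900 × 0.30 = 270 | (210 + 270)/3,000 = 16.0% | 10.0% |

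With equal incidence in kept and removed patients, the percentage does not move, but patients with events still drop out of the subgroups. This matters most for rare serious or unexpected terms.

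**5. The 24-week cut**

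- At least 24 weeks counts as long-term: SAP 6.1, 6.2, 6.3.2 and 7.2 (four sections).
- Strictly more than 24 weeks: SAP 7.3 (four entries) and 7.4 (one entry), five entries in all.

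The versions differ only for a patient at exactly 24 × 7 = 168 days. Protocol 6.1 recommends Visit 3 at 24 ± 2 weeks, which is 154 to 182 days. The disputed value is the centre of that window, so ties are plausible. Their number cannot be derived. A cut inside the visit window is not itself an error.

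**The case against.** The strongest reply is that this is a carried-over label with little effect. The four lines nearly repeat the subgroup list for effectiveness in SAP 6.2. SAP 6.3, SAP 7.4 and protocol 7.3.1 all point away from the effectiveness set, so a careful programmer would probably choose the safety set. Overall incidence, the overall group in item 3 and the 6.3.1 breakdown are untouched. Every safety-set event is still reported by preferred term somewhere, and the study is descriptive with no hypothesis tested.

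HbA1c should also be largely available. Protocol 5.2.2 says it should be collected at baseline and after 12 and 24 weeks, and the flow chart marks the effectiveness endpoints at every visit without the if-applicable flag. Read literally, SAP 3.2 removes only patients with no value at either time.

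Most of this stands, and it limits the size of the problem. A copying slip is likely, though the documents do not say so. It does not remove the conflict: 6.3.2 is the section that defines the analysis, it is explicit in four lines, and nothing ranks 7.4 above it. Protocol 7.4 also makes clear that no test is compulsory, so some missing HbA1c must be expected. The 24-week wording is the smaller of the two points and does not add weight to the first.

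**Conclusion.** The concern holds. SAP 6.3.2 item 3 names the wrong population for four of its five safety groups and contradicts SAP 7.4 on the same tables. The 24-week inequality is also inconsistent, with four sections on one side and two on the other.

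The text conflict is certain; the numerical consequence is not known. The shift in any subgroup incidence is bounded by the share of that subgroup removed. It is probably small if SAP 3.2 excludes only patients lacking both HbA1c values, and larger if either missing value excludes. The percentages in the illustration rest on assumed missingness and assumed event rates. No headline safety result changes. The correction should be made because it concerns the primary objective and the two sections can yield different tables.

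**What to change.** In SAP 6.3.2 item 3, name the safety analysis set in the four subgroup lines, so that they agree with SAP 6.3, 6.3.1 and 7.4. Use one inequality for the 24-week cut in SAP 6.1, 6.2, 6.3.2, 7.2, 7.3 and 7.4. The smaller edit is to bring the five entries in 7.3 and 7.4 into line with section 6, whose short-term and long-term definitions already cover every duration without overlap. The cost is SAP wording only: no new data and no additional tables.

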7.3 PLANNED ANALYSES

7.3.1 Safety analyses

Demographic and baseline characteristics will be summarized descriptively for the entire cohort of eligible patients.

Adverse events (AEs) will be coded according to the latest version of Medical Dictionary for Drug Regulatory Affairs (MedDRA) coding system. Concomitant therapies will be coded according to the latest version of KIMS (Korea Index of Medical Specialties) coding system. The trial database will not be locked until coding is complete.

Safety analyses will be based on all patients treated, i.e. all patients who received at least one dose of Trajenta. However, if data for patients who have been treated with Trajenta beyond the scope of approved label are collected, separate safety analyses will be performed. Safety analyses will be performed based on demographics and baseline characteristics.

Patients lost to follow up will be characterized compared to the remaining patients and reason and time point of loss to follow up will be evaluated.

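### The SAP reports treated excluded patients in one pooled table, so no planned output gives an adverse event incidence for use beyond the approved label alone

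*SAP*

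**What the plan says.** Protocol 7.3.1 sets the safety population broadly: "Safety analyses will be based on all patients treated, i.e. all patients who received at least one dose of Trajenta". It then makes a conditional commitment: "if data for patients who have been treated with Trajenta beyond the scope of approved label are collected, separate safety analyses will be performed".

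SAP 3.1 starts from patients with at least one dose but then narrows the set: "the subjects below shall be excluded from safety analysis set in the following order". Eight reasons follow. They include (1) "Subjects administered Trajenta prior to the contract date", (4) "Subjects who were prescribed for other indications except target indication" and (8) "Subjects who are not Korean". The others are (2) never took the drug, (3) safety follow-up not completed, (5) eligibility violation, (6) dosage or combination outside the listed regimens, and (7) contraindication.

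SAP 6.3.2, item 5, plans one table by preferred term for the excluded patients, introduced by the words "For subjects excluded from the safety analysis set". It covers AE/ADR, serious, unexpected and unexpected serious events, with incidence proportions and 95% confidence intervals. A footnote removes reasons (2) and (3) from it, citing the regulator's guideline. SAP 7.4 lists the same table with the same footnote. Neither place divides it by reason for exclusion.

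**The concern.** The protocol defines the group it wants examined by how the drug was used. The SAP defines its table by absence from the safety set. The two groups overlap but are not the same, because some exclusions say nothing about label use.

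Monitoring safety is the primary objective, and the protocol singles out use beyond the label for its own look. If event rates differ between off-label patients and the other excluded patients, a pooled incidence describes neither. An excess in off-label use would be diluted, and a high pooled figure could not be attributed to it.

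**Working it through.** The documents give no figure to reproduce here: the study is descriptive, and the sample size of 3,000 is a regulatory number. The check is a trace of the eight SAP 3.1 reasons into the item 5 table. The column on label use is a reading of the reasons, since the SAP does not itself define use beyond the label.

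| SAP 3.1 reason | Concerns label use? | In the item 5 table? |
|---|---|---|
| (1) dosed before contract date | No | Yes |
| (2) never took the drug | Not applicable | No (footnote) |
| (3) follow-up failure | No | No (footnote) |
| (4) other indication | Yes | Yes |
| (5) eligibility violation | Mixed | Yes |
| (6) dosage or combination | Yes | Yes |
| (7) contraindication | Yes | Yes |
| (8) not Korean | No | Yes |

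Six of the eight reasons share one numerator and one denominator: three label-related, one mixed and two unrelated to label use. Reason (5) is mixed because the first inclusion criterion (SAP 2.3.1) requires an on-label start, so an off-label start is itself a violation. Missing consent, previous exposure and concurrent trial participation also fall under (5).

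No other output isolates the group. The item 3 subgroups are the safety set, short- and long-term treatment, and previous DPP-4 inhibitor use or not. All lie within the safety or effectiveness sets, from which patients with these exclusion reasons have already been removed.

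The ordering may add to the problem. If each patient is classified by the first reason met, an off-label patient who also meets (1) is counted under (1). One who also meets (3), and not (1), leaves the item 5 table. Protocol 3.2, however, intends to obtain at least adverse event occurrence for patients lost to follow-up where possible, so some data on such patients may exist.

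Illustration of dilution. All values are assumed: 100 patients in the table, event proportion 10% in patients excluded for other reasons, and s the off-label share.

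Pooled proportion = s × p(off-label) + (1 − s) × 10%

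| s | Pooled, p(off-label) = 20% | Pooled, p(off-label) = 30% |
|---|---|---|
| 10% | 11% | 12% |
| 30% | 13% | 16% |
| 50% | 15% | 20% |
| 90% | 19% | 28% |

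For s = 30% and p(off-label) = 20%, the off-label patients alone give 6/30 = 20% (exact 95% CI 7.7% to 38.6%). The pooled row gives (6 + 7)/100 = 13% (exact 95% CI 7.1% to 21.2%). With s = 90% the pooled row is close to the off-label figure, so the harm depends on the mix.

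**The case against.** A reader might infer that the SAP drops the off-label analysis altogether. The documents do not support that. Item 5 does analyse these patients apart from the safety set, by preferred term and event class, with intervals. The protocol does not say that they must be shown apart from every other excluded patient, and the sponsor may have meant item 5 to meet the commitment. What stands against this defence is that the protocol names a group, and no planned table gives that group's incidence.

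A reader might also infer that the ordered list discards second and later reasons. SAP 3.1 fixes an order of exclusion but does not say that further reasons go unrecorded. The ordering problem is therefore conditional.

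Other points on that side are fair:

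- The SAP attributes both the exclusions and the footnote to the regulator's guideline. Whether that guideline prescribes the pooled format cannot be checked from the documents, so a fix should leave the existing table intact.
- Enrolment requires an on-label start and the commitment is conditional, so the group may be small. On the other hand, Protocol 4.2 leaves additional drugs to the physician, while SAP 3.1 (6) lists specific combinations, so patients on unlisted combinations are foreseeable.
- How item 5 is subdivided does not change the estimate in the safety set, and no hypothesis is tested.

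**Conclusion.** The point holds as a lack of separation within a planned table. SAP 6.3.2 (item 5) and 7.4 give one incidence for a group that mixes label-related and unrelated exclusions, which falls short of the analysis described in Protocol 7.3.1.

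This rests on reading reasons (4), (6), (7) and part of (5) as use beyond the label, and on item 5 being the only output for these patients, as the SAP's table list indicates. The loss of off-label patients to reasons (1) and (3) rests further on first-reason classification.

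No magnitude can be drawn from the documents. The dilution figures show the mechanism only. It is a change worth making because it is cheap and concerns the primary objective; it does not threaten the main safety result.

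**What to change.** In the SAP:

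1. In 3.1, flag every exclusion reason that applies to each patient, and code whether a reason (5) violation is an off-label start.
2. In 6.3.2 (item 5) and 7.4, keep the present pooled table as the total and split it into two columns:
   - (a) patients who took at least one dose and have any label-related reason, that is (4), (6), (7) or an off-label start under (5), whatever other reason applies;
   - (b) all other treated excluded patients in the table.
3. Give AE/ADR, serious and unexpected event incidence with 95% confidence intervals for each column.
4. Show treated off-label patients removed for incomplete follow-up on a separate line, with whatever event data are available. The footnoted table then stays unchanged. Patients who never took the drug stay out throughout.

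No new data collection is needed. The cost is modest programming, some extra coding to separate reason (5), and wide intervals if column (a) is small. For example, an assumed 2 events in 10 patients gives 20% with an exact 95% CI of 2.5% to 55.6%.
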